8.2. Setting

8.2.1. Inclusion Criteria

Physicians meeting the following criteria will be invited to participate in the chart review study:

- Specialty in oncology.
- Access to complete medical records for at least one patient with advanced RCC who meets the patient eligibility criteria.

Eligible oncologists will be asked to select up to three patients meeting the following criteria for inclusion in the chart review study:

- Confirmed diagnosis with advanced RCC.
- Treated with first-line axitinib/IO combination therapy at or after diagnosis.
- Experienced at least one AE (ie, diarrhea, fatigue, nausea, hypertension, and palmar-plantar erythrodysesthesia [hand-foot syndrome]) while treated with axitinib/IO combination therapy.

- Age 18 years or older at the time of advanced RCC diagnosis.
- Initiated axitinib/IO combination therapy at least 3 months prior to the start date of medical chart abstraction to ensure sufficient follow-up time.

In the event that an oncologist has more than three eligible patients, the electronic case report form (eCRF) will have an underlying program that requires the oncologist to select patient charts based on a randomized sequence of letters. Specifically, the program will produce a random letter and request the oncologist to pull the first eligible patient chart with the last name that corresponds to the random letter. If there are no eligible patients whose last name begins with the first letter in the sequence, then the next letter in the order of the sequence will be shown. The random process will repeat for each new patient chart to be completed by the oncologist, until chart abstraction is completed for three eligible patients or until the physician has identified all eligible patients.

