8.5. Study Size

Approximately 200 oncologists may be recruited by the physician panel vendor to abstract medical charts. AG anticipates to obtain data from the medical charts of 400-600 patients with advanced RCC. No formal sample size computation was performed as all statistical analyses are descriptive in nature and no hypotheses are being tested.

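### A listed AE is required before a chart can be sampled, and the random draw runs only above three such patients, so management-strategy and serious-AE shares depend on how completely each oncologist finds AE cases

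*Combined protocol and SAP*

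**What the plan says.** Section 8.2.1 lists as an inclusion criterion: "Experienced at least one AE (ie, diarrhea, fatigue, nausea, hypertension, and palmar-plantar erythrodysesthesia [hand-foot syndrome]) while treated with axitinib/IO combination therapy". For the choice of charts it states: "Eligible oncologists will be asked to select up to three patients meeting the following criteria".

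The letter program has a condition attached: "In the event that an oncologist has more than three eligible patients". When it runs, it shows a random letter and asks the oncologist to "pull the first eligible patient chart with the last name that corresponds to the random letter". If no eligible patient matches, the next letter is shown. The process repeats "until chart abstraction is completed for three eligible patients or until the physician has identified all eligible patients".

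Section 8.5 gives the scale: "Approximately 200 oncologists may be recruited by the physician panel vendor to abstract medical charts", with 400-600 patient charts expected.

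The physician variables in 8.3.1 include advanced RCC patients seen per year and the percentage prescribed first-line axitinib/IO in the past year. They do not include the number of eligible patients, the number of charts checked for an AE, or whether the draw was used. Section 8.9 discusses selection bias only for physicians who choose to take part. It also says that entries cannot be audited against the records.

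**The concern.** AE status enters before sampling. The frame is the set of patients the oncologist identifies as AE-positive, and the draw, when it runs, operates inside that frame. With three or fewer such patients there is no draw. No step asks for a list of all axitinib/IO starters or describes how AE cases are to be located in the records.

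An AE that led to a dose change, an interruption, a discontinuation or an admission plausibly leaves a clearer trace than mild nausea that needed no action. If so, the chance of entering the study depends on management and seriousness. Objective 2 reports the proportion using each of eight strategies, beginning with no action, and Objective 1 reports seriousness. A fair draw within the frame would not correct this. Section 6 says the study could help show that AEs can be mitigated through axitinib modification, so the balance between modified and unmodified cases bears on its message.

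**Working it through.** **1. The plan's own figure.** 200 oncologists × 3 charts = 600, the upper end of the range in 8.5. The lower end, 400, is 400 / 200 = 2 charts per oncologist. The stated size is consistent. The study is descriptive, so there is no power calculation to reproduce.

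**2. How many charts could fall outside the draw.** Assume each of the 200 oncologists supplies at least one chart, and let *x* be the largest number who can supply three. Then 3*x* + (200 − *x*) = *N*, so *x* = (*N* − 200) / 2.

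- *N* = 400: *x* = 100, so at least 400 − 300 = 100 charts (25%) come from oncologists supplying fewer than three.
- *N* = 500: *x* = 150, so at least 500 − 450 = 50 charts.
- *N* = 600: *x* = 200, so the minimum is 0.

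If the draw rule is followed as written, an oncologist supplying fewer than three charts had no draw. These are lower bounds, because an oncologist with exactly three eligible patients has no draw either.

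**3. Effect of uneven listing.** Let *m* be the true share of AE patients managed by a treatment change. Let *r* be the chance that a no-action patient is listed, relative to a managed one. Both are assumed; the documents give neither.

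Reported managed share = *m* / (*m* + *r*(1 − *m*)). For example, *m* = 0.5 and *r* = 0.75 give 0.5 / (0.5 + 0.375) = 0.571.

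| *r* | true 30% | true 50% | true 70% |
|---|---|---|---|
| 1 | 30.0% (0) | 50.0% (0) | 70.0% (0) |
| 0.9 | 32.3% (+2.3) | 52.6% (+2.6) | 72.2% (+2.2) |
| 0.75 | 36.4% (+6.4) | 57.1% (+7.1) | 75.7% (+5.7) |
| 0.5 | 46.2% (+16.2) | 66.7% (+16.7) | 82.4% (+12.4) |

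**4. What each ratio requires.** If every managed patient is listed, the overlooked fraction of eligible patients is 1 − [*m* + *r*(1 − *m*)]. At *m* = 0.5 this is 5%, 12.5% and 25% for *r* = 0.9, 0.75 and 0.5. The formula applies *r* to all charts. If half the charts come from complete lists with the same true share, the 7.1-point shift falls to about 7.1 × 0.5 = 3.6 points.

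**5. Comparison with sampling error.** The 95% half-width at 50% is 1.96 × √(0.25 × *D* / *N*), where *D* = 1 + (*k* − 1) × ICC and *k* is charts per oncologist. With an assumed ICC of 0 to 0.1, it is 4.9-5.1 points at *N* = 400 (*k* = 2) and 4.0-4.4 points at *N* = 600 (*k* = 3). With *r* applied to all charts, the shift exceeds sampling error at about 0.75 or lower and is smaller than it at 0.9.

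**6. What the data could show.** Multiplying the two caseload variables in 8.3.1 gives a rough number of treated patients per year. It refers to the past year, whereas the index window opens in May 2019 (8.1). It cannot show which AE-positive patients were left out.

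**The case against.** A reader might infer that oncologists work from memory and that over-sampling of actively managed cases will occur. The documents do not support that. Section 8.2.1 speaks of an oncologist who has more than three eligible patients, requires access to complete records, and never mentions recall. An oncologist with three or fewer eligible patients who submits all of them provides a census, with no selection. Above three, the letter-by-letter wording can be read as checking eligibility during the draw, which is already close to the order proposed here. All of this stands. What remains is that nothing requires or verifies a complete listing.

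A reader might also infer that Objectives 2 and 3 are affected throughout. They are not. Time to resolution is analysed separately by strategy (8.7.4), and dose-reduction size and interruption duration are reported only among patients who had them (8.7.3). Over-representing managed patients is largely conditioned out of these results.

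A third inference is that nothing collected could hint at the problem. The eCRF is still to be developed (8.4) and might capture an eligible count in order to trigger the program, and 8.3.1 gives a rough caseload. But no listed variable covers the eligible count, charts screened or use of the draw.

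Finally, 8.9 limits the strategy proportions to AEs that needed healthcare intervention. That concession concerns AEs missing from the chart or never reported. It does not cover AEs that are recorded but whose patients are not put forward.

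**Conclusion.** The concern holds as a risk to marginal shares: the distribution of management strategies in Objective 2 and the serious-AE share in Objective 1. It arises only if listing is incomplete and favours AEs that led to action. The documents neither show that this happens nor prevent it.

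The size is unknown. Under the assumed ratios it runs from zero to about 17 points at a true 50% share, and charts from oncologists with complete lists dilute it. Changing the procedure is still justified, because the order can be made less dependent on the outcome at little cost and the screening counts are otherwise missing.

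**What to change.** In 8.2.1, run the letter draw for every oncologist, whatever the number of patients, over all patients who started first-line axitinib/IO in the study window and without regard to AEs. Check the AE criterion only after a chart is drawn. Log a drawn chart without a listed AE as a one-line screen-out and draw the next, until three charts are completed or the list ends. Add to 8.3.1, and report per oncologist, the number of treated patients listed, charts drawn and charts screened out. Add patient-level selection to the limitations in 8.9. The study population stays restricted to patients with a listed AE.

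The cost is eCRF screening logic, a few lines of protocol text and some short chart checks. If 60-90% of treated patients have a listed AE (assumed; the documents give no figure), three completed charts need 3 / 0.9 = 3.3 to 3 / 0.6 = 5 draws. Section 8.4.1 already allows the protocol and eCRF to be updated after the pilot.

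The change reduces the risk but does not remove it: the oncologist still builds the list of treated patients and judges each screen-out, and entries cannot be audited.

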Yet, recent advancements in immuno-oncology (IO) therapeutic agents have changed the treatment paradigm for advanced RCC. IO therapies work by blocking immune checkpoints (eg, programmed death-1 [PD-1]/PD-ligand 1 [PD-L1]) and restoring tumor-specific T-cell-mediated immune responses,^{16,17} and have demonstrated antitumor activity and durable responses in patients with advanced RCC.^{18,19} Specifically, the KEYNOTE-426 trial demonstrated that treatment-naïve advanced RCC patients who were treated with axitinib in combination with pembrolizumab had significantly longer overall survival, progression-free survival, and objective response rate compared to sunitinib,²⁰ leading to US Food and Drug Administration (FDA) approval of axitinib in combination with pembrolizumab for first-line advanced RCC treatment in April 2019. In addition, the JAVELIN Renal 101 trial showed significantly longer progression-free survival among advanced RCC patients who received avelumab plus axitinib than with sunitinib in first-line,²¹ leading to FDA approval of axitinib in combination with avelumab for first-line advanced RCC treatment in May 2019.

While axitinib has generally demonstrated a favorable tolerability profile in real-world studies,^{22,23} there is currently limited information on the real-world adverse event (AE) profile of axitinib in combination with IO therapies. In addition, the effect of dose reductions and treatment interruptions used to manage and resolve AEs occurring among patients with advanced RCC who use axitinib in combination with IOs is not well understood. Given this gap in the literature, AG will conduct a physician panel-based chart review to describe how dose reductions or treatment interruptions related to axitinib (in combination with IO therapy including avelumab or pembrolizumab) can be implemented to potentially manage and resolve AEs occurring among patients with advanced RCC. In this way, the study could help demonstrate that AEs associated with axitinib may be mitigated without excess use of healthcare resource use or additional treatment burden to patients beyond modifications related to axitinib.

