8. RESEARCH METHODS

8.1. Study Design

A retrospective physician panel-based chart review study in the US will be conducted. The index date will be defined as the initiation of first-line axitinib (used in combination with IO therapy) on or after May 2019, which marks FDA approval of axitinib in combination with avelumab for first-line advanced RCC treatment. The baseline period will be defined as the 12-month period prior to the index date. The observation period will be defined as the time from index date to the earliest of initiation of a second line therapy, death, loss to follow-up, or date of chart abstraction. During the observation period, onset, management, and resolution of AEs will be assessed. The study design scheme is depicted in Figure 1.

Figure 1. Study Design Scheme

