8.2.2. Exclusion Criteria

There are no exclusion criteria for this study.

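### The patient selection list in section 8.2.1 omits the May 2019 start that section 8.1 requires, and the plan neither screens for nor records treatment inside an interventional trial

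*Combined protocol and SAP*

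**What the plan says.** Section 8.1 fixes the start of the study window: "The index date will be defined as the initiation of first-line axitinib (used in combination with IO therapy) on or after May 2019". The baseline period, the observation period and the time to AE onset are all counted from that date.

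The list from which oncologists choose charts is in section 8.2.1. Its treatment criterion is "Treated with first-line axitinib/IO combination therapy at or after diagnosis". Its only timing rule for treatment start is "Initiated axitinib/IO combination therapy at least 3 months prior to the start date of medical chart abstraction to ensure sufficient follow-up time". Section 8.2.2 adds: "There are no exclusion criteria for this study".

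Section 6 gives the purpose. It states that "there is currently limited information on the real-world adverse event (AE) profile of axitinib in combination with IO therapies", and says the chart review is meant "to describe how dose reductions or treatment interruptions related to axitinib (in combination with IO therapy including avelumab or pembrolizumab) can be implemented".

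Section 8.3.2 collects the date on which the combination was started. Nothing in sections 8.3.1 to 8.3.4 records whether it was given inside an interventional trial, and the limitations in section 8.9 do not mention trial participants.

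**The concern.** There are two separate gaps.

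The first is a mismatch between design and selection list. The three-month rule bounds the latest start but not the earliest. A patient who started before May 2019 can satisfy every item in section 8.2.1 and still have no index date under section 8.1. Each oncologist contributes at most three charts, so such a patient may use a slot that a valid patient could have filled.

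The second concerns what the results describe. The main outputs are the mix of management strategies and the time to resolution by strategy. If some patients had dose changes or AE recording governed by a trial protocol, those outputs would partly describe that protocol and not the physician's own practice. Section 8.6 says physicians keep no decoding key, and section 8.9 says entries cannot be audited or queried. A fact not asked for at abstraction is therefore lost.

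**Working it through.** **Step 1. Compare the entry windows.**

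- Section 8.1: earliest start May 2019.
- Section 8.2.1: no earliest start; latest start three months before abstraction.
- Section 5: data collection from 30 November 2020 to 31 January 2021.

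Taking 1 May 2019 as the start (the protocol gives only the month), the intended window is 1 May 2019 to 30 August 2020, about 16 months, if the three months are counted back from the first day of collection. Counted back from the last day, it runs to 31 October 2020, about 18 months. The window in section 8.2.1 has the same end and no beginning.

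A concrete case comes from section 6, which dates approval of axitinib with pembrolizumab to April 2019. A patient who started that month, with one listed AE and advanced RCC diagnosed as an adult, passes section 8.2.1 and fails section 8.1.

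**Step 2. Can early starters be found later?** Yes. The initiation date is a listed variable in section 8.3.2, so they can be dropped at analysis. The loss is the chart slot. Where an oncologist has more than three apparently eligible patients, the random-letter draw may pick an early starter in place of a valid patient, and no replacement rule is described.

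**Step 3. Can trial-treated patients who started from May 2019 onward be found later?** No listed variable would do it. The start date does not separate them. Practice setting (section 8.3.1) describes the physician, not the patient's treatment. Section 8.4 allows open-ended fields, but none is assigned to this question.

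**Step 4. Planned size.** Section 8.5 expects 400-600 patients from about 200 oncologists, each with up to three charts: 200 × 2 = 400 and 200 × 3 = 600. The average of two charts behind the lower figure is inferred, not stated. There is no formal sample size for the fix to alter.

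**Step 5. Possible shift (illustration only).** Let s be the trial-treated share and d the difference, in percentage points, between trial and routine use of a given strategy. Then

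observed proportion − routine proportion = s × d.

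Neither s nor d is in the documents. Assume s from 2% to 20% and d from 10 to 30 points:

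- Patients involved: 0.02 × 400 = 8, up to 0.20 × 600 = 120.
- Smallest shift: 0.02 × 10 = 0.2 points.
- Middle case: 0.10 × 20 = 2.0 points.
- Largest shift: 0.20 × 30 = 6.0 points.

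For scale, the 95% half-width for a proportion of 50%, ignoring clustering by oncologist, is 1.96 × √(0.25/400) = 4.9 points, or 1.96 × √(0.25/600) = 4.0 points. With d = 30, the share would have to exceed 4.9/30 = 16% at 400 patients, or 4.0/30 = 13% at 600, before the shift outgrew that half-width.

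**The case against.** The best defence on the date is that sections 8.1 and 8.2.1 are to be read together. A patient without a valid index date cannot be analysed, the initiation date is collected, and section 8.8 provides automatic date checks in the eCRF that could enforce the limit. This largely stands. It reduces the date gap to an alignment of wording plus some wasted slots, since the plan does not say that the date checks apply this limit before a chart is drawn.

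On trial participation, the defence is that the protocol is only silent, that the documents do not show any such patient in panel oncologists' charts, and that no passage says how trial management would differ. This also stands as far as size and direction are concerned. It does not supply the missing variable.

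Four stronger readings are tempting and are not supported:

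- *That patients from the two first-line trials named in section 6 would contaminate the results beyond repair.* Those trials led to the April and May 2019 approvals. Their participants who started before May 2019 fall outside section 8.1 and can be removed by start date.
- *That no ineligible patient could be removed afterwards.* This holds only for trial-treated patients who started from May 2019 onward.
- *That the missing date is what lets trial patients in.* Adding it would not keep out those treated later. The two gaps need separate repairs.
- *That trial patients would cluster in academic practices.* Nothing in the documents says so, and the cap of three charts limits what any one oncologist contributes.

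**Conclusion.** Both omissions are plain in the text, and they differ in weight.

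The missing May 2019 start is an inconsistency between sections 8.1 and 8.2.1. It is repairable in the data at the price of some chart slots, whose number the documents do not give.

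The absence of any trial restriction or flag matters more, because it cannot be repaired once collection closes. A plan followed as written could mix protocol-driven AE management into the strategy and resolution results unnoticed. The 0.2 to 6.0 point range rests wholly on assumed shares and differences. Its low end is negligible, and its high end needs both a large share and a large difference. The case for acting is therefore that the remedy is cheap and the omission irreversible, not that a large bias has been shown.

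The eCRF itself is not among the documents, so this conclusion takes section 8.3 as the full list of what is collected.

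**What to change.** 1. Repeat the section 8.1 limit, start on or after May 2019, among the patient criteria in section 8.2.1, and check it at eCRF screening before a chart is drawn.
2. Add a screening question on whether the axitinib/IO combination was given within an interventional trial. Then either exclude such patients in section 8.2.2, or keep the answer as a variable in section 8.3 and report the management and resolution results without them. The second option keeps the charts and shows whether the results depend on them.

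Section 8.4.1 already allows the eligibility criteria and eCRF to be revised after the pilot, so both changes fit the planned process. The cost is one or two extra screening questions, a wording alignment and a small number of charts made ineligible. No stated figure in the plan changes.

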5. MILESTONES

Milestone	Planned Date
Start of data collection	30 November 2020
End of data collection	31 January 2021
Final study report	31 July 2021

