7. RESEARCH QUESTION AND OBJECTIVES

The specific objectives of the study are as follows:

1. Describe incident AEs experienced among patients with advanced RCC who received first-line axitinib in combination with IO therapies.
 - Type and seriousness of AEs (ie, diarrhea, fatigue, hypertension, nausea, palmar-plantar erythrodysesthesia [hand-foot syndrome]).

- Proportion of patients who experienced repeated AEs.
- Time from treatment initiation to AE onset, overall and by type and seriousness of AEs.

2. Among patients with advanced RCC who developed incident AEs while receiving first-line axitinib in combination with IO therapies, characterize and describe management strategies for AEs, stratified by type and seriousness of AEs.

- Proportion of patients who used each of the following management strategies:
 - No action for axitinib and IO therapy;
 - No action for axitinib, but treatment modification for IO therapy (ie, treatment interruption, treatment discontinuation);
 - Axitinib dose reduction, but no action for IO therapy;
 - Axitinib treatment interruption, but no action for IO therapy;
 - Axitinib treatment discontinuation, but no action for IO therapy;
 - Axitinib dose reduction, and treatment modification for IO therapy;
 - Axitinib treatment interruption, and treatment modification for IO therapy;
 - Axitinib treatment discontinuation, and treatment modification for IO therapy.
- Average axitinib dose reduction (absolute and percentage change), where applicable.
- Duration of treatment interruption, where applicable.

3. Assess the frequency of and time to AE resolution (from AE onset and initiation of management strategy, separately) among patients with advanced RCC who developed incident AEs while receiving first-line axitinib in combination with IO therapies according to different management strategies implemented, stratified further by type and seriousness of AEs, as allowed by sample size.

[figure not shown]
The above objectives will also be conducted for repeated AEs of the same type.

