8.7.2. Analysis of AEs

Type and seriousness of AEs will be tabulated and described using frequency and proportions, separately by type of therapy (ie, type of IO therapy given in combination with axitinib). In addition, the proportion of patients who experienced repeated AEs of the same type will be summarized overall and by type of AE. For each type and seriousness of AE, time from index date to onset of AEs will be summarized using means (\pm SD) and medians (IQR). Furthermore, the time between the first AE and the first repeated AE of the same type will be calculated.

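### Time to AE onset in Section 8.7.2 is biased short, because only onsets seen by chart abstraction are summarised and time since initiation varies from 3 to about 19–21 months

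*Combined protocol and SAP*

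**What the plan says.** - **Output (Section 7, Objective 1):** "Time from treatment initiation to AE onset, overall and by type and seriousness of AEs".
- **Entry (Section 8.2.1):** the patient must have "Experienced at least one AE" of five listed types while on the combination, and must meet the 3-month rule: "Initiated axitinib/IO combination therapy at least 3 months prior to the start date of medical chart abstraction to ensure sufficient follow-up time".
- **Window (Sections 8.1 and 5):** the index date is "initiation of first-line axitinib (used in combination with IO therapy) on or after May 2019". Observation ends at "the earliest of initiation of a second line therapy, death, loss to follow-up, or date of chart abstraction". Data collection opens on "30 November 2020" and closes on 31 January 2021.
- **Analysis (Section 8.7.2):** "For each type and seriousness of AE, time from index date to onset of AEs will be summarized using means (\pm SD) and medians (IQR").

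Kaplan-Meier is planned only for AE resolution (Section 8.7.4). No onset analysis by length of follow-up or start date is planned. The limitations in Section 8.9 mention neither selection on having had an AE nor unequal follow-up.

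**The concern.** An onset reaches the Section 8.7.2 summary only if it happened before that patient's chart was abstracted. A patient who started 3 months earlier can contribute only onsets within 3 months; one who started 18 months earlier can contribute onsets up to 18 months. Late onsets are therefore under-represented, most of all among recent starters.

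The missing late onsets are of two kinds:

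- **Right truncation.** A patient with none of the five AEs by abstraction is not in the study at all.
- **Ignored censoring.** A patient enrolled for one AE type may later develop another. That patient is in the data and is censored for the second type, but a mean or median of observed onsets leaves the censoring out.

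At stake is a named Objective 1 output. Early-onset AE types are barely affected and late-onset types are shortened, so the differences between types shrink. The reported number also depends on when patients happened to start.

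**Working it through.** **Inputs from the documents.** Minimum time since initiation is 3 months (up to about 5 if the chart is abstracted at the end of the collection period). Maximum is about 19 months (1 May 2019 to 30 November 2020) to about 21 months (to 31 January 2021). Entry needs any one of five AE types.

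**Assumptions, because the documents give no figures.** Time since initiation F is uniform on 3–20 months. Onset T is exponential with rate λ = ln 2 / median. There is no discontinuation at first. The plan states no onset time, so there is no figure to reproduce.

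**Step 1: share of onsets not seen by abstraction.**

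P(T > F) = (e^(−3λ) − e^(−20λ)) / (17λ)

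- Median 2: λ = 0.3466; (0.3536 − 0.0010)/5.892 = 6.0%.
- Median 6: λ = 0.1155; (0.7071 − 0.0992)/1.964 = 31%.

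**Step 2: median that would be reported.** The observed density is proportional to λe^(−λt) × P(F ≥ t), where P(F ≥ t) is 1 up to 3 months and (20 − t)/17 after that. Solving for the median:

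| True median (months) | Not seen | Observed median |
|---|---|---|
| 1 | 1.1% | 0.98 |
| 2 | 6.0% | 1.83 |
| 4 | 19% | 2.99 |
| 6 | 31% | 3.68 |

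A true 3-fold contrast (2 versus 6 months) appears as 3.68/1.83 = 2.0-fold. Moving the upper limit of F to 19 or 21 months changes 3.68 to 3.59 or 3.76.

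**Step 3: sensitivity (simulation).**

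- Mix of starters, true median 6: follow-up of 3–6 months gives 1.94 and follow-up above 17 months gives 5.03. If all follow-up were 3–9 months, 6 is seen as 2.43.
- Shape: lognormal onset (log SD 1) turns 4 into 3.11 and 6 into 4.05. Weibull onset with shape 0.7 turns 3 into 1.92.
- Discontinuation with median 11 months, counting only on-treatment AEs: for underlying medians of 3 and 6, the target and observed medians are 2.35 versus 2.09 and 3.88 versus 2.94.

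**Step 4: how much is truncation and how much is ignored censoring.** A patient with an observed onset of a given type always meets the entry rule. The type-specific figures in Step 2 therefore hold whatever the other types do; only the cause changes. With k independent types, all with median 6, the share of starters excluded is Step 1 with kλ in place of λ. Dividing this by 0.3095 gives the share of a type's unseen onsets that belong to excluded patients.

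- Two types: 12.5% excluded; 0.1248/0.3095 = 40%, so 60% of unseen onsets are in enrolled patients.
- Five types: 1.8% excluded; 0.0180/0.3095 = 6%, so 94% are in enrolled patients. The median time to first AE is then hardly affected (1.20 true, 1.17 observed).

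**Step 5: what a fixed horizon H delivers.** Among patients who started at least H months before abstraction, the median of onsets within H is −ln(1 − ½(1 − e^(−λH)))/λ, whatever the follow-up mix.

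| Horizon | True 2 | True 6 | Ratio |
|---|---|---|---|
| Current plan | 1.83 | 3.68 | 2.0 |
| 12 months | 1.96 | 4.07 | 2.1 |
| 6 months | 1.66 | 2.49 | 1.5 |

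Simulation returned these targets (4.07 at 12 months and 2.49 at 6 months for a true median of 6).

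**Step 6: sample retained at 12 months.** The share of starters is (20 − 12)/17 = 47%. Among sampled AE patients at a true median of 6, where 16.3% of onsets are unseen in this subset, it is 0.4706 × (1 − 0.163)/(1 − 0.310) = 57%. Those whose onset also falls within 12 months are 0.4706 × 0.75/0.690 = 51%.

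**The case against.** The best defence is that these may be early AEs. If median onset is about 1 month, the reported 0.98 is right for any practical purpose. Three months is a floor, not the typical follow-up. AEs count only while the patient is treated, so an onset that never happens because treatment stopped is outside the target. The study is descriptive and tests no hypothesis (Section 8.5). All of this stands, and it makes the size uncertain. It does not change the direction, and the plan offers no onset data to show that the early-onset case applies.

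A second objection concerns cause. A reader might infer that every missing late onset belongs to an unsampled patient, so that no censoring method could help. The entry rule does not support that. It needs any one of five AEs, and Step 4 shows that many, possibly most, late type-specific onsets would fall in patients already enrolled. The split rests on independence and on every patient eventually having every type; fewer types per patient would raise the share excluded. For time to first AE the inference is closer to right: every enrolled patient has the event, so Kaplan-Meier on this sample would adjust nothing.

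A third objection is that the 12-month horizon barely restores the contrast between types (2.1-fold against 2.0-fold). That is correct. Its merit is a defined quantity that does not move with the mix of start dates.

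**Conclusion.** The point holds. As planned, onset times are biased short by an amount that depends on the spread of start dates, and the plan does not say so. Under exponential onset and uniform 3–20 month follow-up, the bias is negligible at a median of 1 month, modest at 2 (seen as 1.8) and material at 4 to 6 (seen as 3.0 and 3.7). It is smaller with discontinuation and larger with a heavy tail or mostly recent starters. These sizes are illustrations, since the documents fix only the follow-up window. If the May 2019 start in Section 8.1, which is not listed among the criteria in Section 8.2.1, were not enforced, follow-up could be longer and the bias somewhat smaller.

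Two stronger readings are not supported:

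- A reader might infer that comparisons of onset time between IO agents are distorted. Section 8.7.2 splits type and seriousness by IO agent, but plans onset time only by AE type and seriousness. Nothing in the documents shows different uptake of the two agents over time.
- A reader might take the 3-month rule as a claim that onset time is fully observed. Section 8.2.1 speaks of follow-up in general and makes no such claim.

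**What to change.** 1. **Section 8.7.2, main onset summary.** Among patients who initiated at least 12 months before abstraction, summarise onsets within 12 months, labelled *time to onset among AEs occurring within 12 months*. A 6-month version can be supportive only, because it compresses differences between AE types further.
2. **Section 8.7.2, all-patient summary.** Keep it, labelled *among AEs observed by abstraction*.
3. **Optional.** For first AE onset, add a right-truncation (reverse-time product-limit, Lynden-Bell) estimate using each patient's index-to-abstraction interval. In simulation (n = 500, 300 replicates, a single onset per patient) it gave 2.98 against a naive 2.49 for a true median of 3, and 5.28 against 3.71 for a true median of 6. It estimates onset given occurrence within about 20 months (5.18 in the last case), not the unrestricted median.
4. **Section 8.3.** Record the abstraction date. Section 8.1 relies on it, but it is not among the listed variables.
5. **Section 8.9.** State that onset times are conditional on an AE before abstraction, that late onsets are under-represented, and that later AE types in enrolled patients are censored.

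**Cost.** Wording and one date field; eligibility and recruitment are unchanged. About 47–57% of sampled patients would qualify by start date for the 12-month summary, roughly 188 (0.47 × 400) to 342 (0.57 × 600) of the anticipated charts. The horizon removes dependence on the abstraction date but not on loss to follow-up before 12 months, so report the number lost. Only sampling starters regardless of AE would remove the conditioning altogether, and that is a different study.
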